2.2 Study Design

This is a randomized, double-blind, placebo-controlled, oral dose, phase 2 study to evaluate the dose response of ASP0367 on functional improvement relative to placebo, safety and tolerability in participants with PMM. Efficacy (i.e., functional improvement) will be assessed by a functional motor test, 6MWT. The study consists of the following portions: screening (4 weeks); double-blind treatment period with 2 doses of ASP0367 vs matching placebo (24 weeks); and follow-up (4 weeks).

A 24-week treatment analysis of efficacy and safety will be the primary focus of this study. Since participants enrolled and participated in the study prior to implementation of protocol version 9.0, which removes the 52-week OLE period, they may have a treatment duration of up to 76 weeks, a separate analysis will be conducted up to 76 weeks and follow-up as per available data.

2.3 Randomization

Approximately 66 participants will be enrolled. At randomization, participants will be randomly placed into 1 of 3 arms (30 mg ASP0367, 75 mg ASP0367 or placebo; n = 22 for each arm) at a ratio of 1:1:1. Stratified randomization by site group (2 level: Mayo clinic_Minnesota; Non-Mayo clinic_Minnesota) will be applied, if there are any participants from in the Mayo site group.

3 SAMPLE SIZE

The sample size of this study was determined from feasibility and statistical perspectives. From the statistical perspective, 57 participants (19 participants in each group) will provide > 80% power to detect a difference of 45 meters in 6MWT between ASP0367 and placebo at a 2-sided significance level of 0.10 assuming a common standard deviation of 55.0 meters.

The 45-meter difference in 6MWT under the 24-week treatment is assumed based on the results of the MMPOWER-2 study of elamipretide [Cohen et al, 2018].

Considering the interim analysis, 60 participants will be required to maintain > 80% power in the efficacy analysis, and assuming an approximately 10% study discontinuation (drop out) rate during the double-blind treatment period, 66 participants are required to be randomized. This sample size supports an evaluation of proof of concept.

4 ANALYSIS SETS

In accordance with ICH recommendations in guidelines E3 and E9, the following analysis sets will be used for the analyses.

4.1 Safety Analysis Set

The SAF consists of all participants who receive at least 1 dose of ASP0367. The SAF only includes participants who were randomly assigned to ASP0367 in DB part or participants who were randomly assigned to placebo in the DB part and continued into the OLE part. Participants who were randomly assigned to placebo and discontinued the study in the DB part are not included in the SAF, even if they erroneously received ASP0367 during the DB part.

The SAF will be used for all summaries of the safety data.

5 EFFICACY AND SAFETY ENDPOINTS

5.1 Exploratory Endpoints

5.1.1 6-minute Walk Test

The 6MWT will be performed indoors, along a long, flat, straight, enclosed corridor with a hard surface that is seldom traveled. The total distance walked by a participant, as well as distance per minute will be calculated by rounding to the nearest meter and recorded. The 6MWT will be video recorded for quality purposes.

Participants will be asked to wear comfortable clothing and appropriate shoes for walking. A light meal is acceptable before early morning or early afternoon tests. Participants will be recommended not to have exercised within 2 hours prior to beginning of the test. A "warm up" period before the test will not be performed. Participants will sit at rest in a chair located near the starting position for at least 10 minutes before the test starts. The test will be performed at weeks 0, 4, 12, 24, 36, 52, 64 and 76.

5.1.2 5 Times Sit To Stand (5XSTS)

For the 5XSTS, the participant will be instructed to sit with arms folded across their chest and with back against the chair and will be asked to stand up and sit down 5 times in a row, as quickly as he/she can. The instructor will make sure that the participant will stand up fully and try not to let his/her back touch the chair between each repetition. The duration from the time instructor indicates "Go" until the time participant's body touches the chair following the fifth repetition will be recorded. If participant is unable to complete the first sit to stand independently, without use of arms, the test will be terminated. The test will be performed at weeks 0, 4, 12, 24, 36, 52, 64 and 76.

5.1.3 Quality of Life in Neurological Disorders (Neuro-QoL)

The Neuro-QoL is a measurement system that evaluates and monitors the physical, mental and social effects experienced by adults and children living with neurological conditions. Participants will report Neuro-QoL Item Bank v1.0 Fatigue Short Form and Lower Extremity Function (Mobility) Short Form, which consists of 8 items each. Neuro-QoL will be performed at weeks 0, 4, 12, 24, 36, 52, 64 and 76.

5.1.4 Modified Fatigue Impact Scale (MFIS)

The Modified Fatigue Impact Scale (MFIS) is a modified form of the Fatigue Impact Scale. The questionnaire specifically measures how fatigue impacts the lives of those affected by fatigue-like symptoms.

There are 21 items in the scale measuring 3 domains of fatigue including physical, cognitive and psychosocial functioning. MFIS will be performed at weeks 0, 4, 12, 24, 36, 52, 64 and 76.

5.1.5 Patient Global Impression of Change (PGIC)

The Patient Global Impression of Change (PGIC) scale evaluates the participant's most bothersome symptom and assesses if there has been an improvement or decline in clinical status. The participant will rate his/her change on a 7-point scale. The PGIC score will be evaluated at weeks 4, 12, 24, 36, 52, 64 and 76.

5.1.6 The Patient Global Impression of Severity (PGIS)

The Patient Global Impression of Severity (PGIS) is a questionnaire designed to assess patient's impression of disease severity. The questionnaire asks the participant to best describe the severity of the participant's most bothersome pre-defined symptom over the past week. The PGIS score will be assessed at weeks 0, 4, 12, 24, 36, 52, 64 and 76.

5.1.7 European Quality of Life 5-dimension, 5-level questionnaire (EQ-5D-5L)

The EQ-5D-5L is a brief, generic health-related quality of life assessment that can also be used to incorporate participant preferences into health economic evaluations. The EQ-5D-5L descriptive system comprises the following 5 dimensions: mobility, self-care, usual activities, pain/discomfort and anxiety/depression. Each dimension has 5 response levels: no problems, slight problems, moderate problems, severe problems and extreme problems/unable to perform the activity. In addition, it does record the patient's self-rated health on a vertical visual analogue scale with response options ranging from 0 (worst imaginable health) to 100 (best imaginable health). The EQ-5D-5L will be assessed at weeks 0, 4, 12, 24, 36, 52, 64 and 76.

5.2 Safety Endpoints

5.2.1 Treatment Emergent Adverse Events (TEAEs)

AE collection begins after the ICF has been signed and continues until the follow up visit or 28 days after the final IP administration or when the participant is determined to be a screen failure. A TEAE is defined as an AE observed after starting administration of the ASP0367 to 28 days after the last dose of ASP0367.

An IP-related TEAE is defined as any TEAE with a causal relationship of "yes" by the investigator.

5.2.2 Vital signs

Vital signs including blood pressure, pulse rate and body temperature will be assessed at each visit scheduled in the protocol.

5.2.3 12-lead Electrocardiogram (ECG)

- A standard 12-lead ECG will be conducted using both a central ECG reading laboratory and local ECG reading. ECGs at weeks 2 and 8 will be performed at the participant's home by a qualified healthcare provider from the home healthcare vendor. In case the home healthcare visit is not feasible, the visit can be conducted at the study site.
- ECGs will be recorded in triplicate (3 separate ECGs, 5 minutes resting prior to first ECG and at least 1 minute apart per time point), prior to blood draw and transmitted electronically for central reading. The mean of the triplicate ECG from central and local read should be used for treatment decisions and AE reporting.
- If the mean triplicate QTcF is > 500 msec at any time point, one follow-up triplicate ECG may be performed on the same day. If the follow-up mean QTcF is ≤ 500 msec, the participant may proceed with IP. If the follow-up mean QTcF > 500 msec is confirmed, then the participant must discontinue IP.
- An ECG will also be performed within 24 hours of any of these events: an elevation of cTnI above the ULN (see Appendix 10.9 in the protocol for reference range), or when there is an elevation of cTnT above the ULN (see Appendix 10.9 in the protocol for reference range) or above the participant's baseline value if it was elevated, or when a participant has any signs or symptoms reflecting cardiac involvement, inclusive of new onset shortness of breath. If the ECG is within normal limits, a repeat of the abnormal troponin value (cTnI or cTnT) should be obtained. For any of the situations above, it

may be required to interrupt or discontinue further administration of IP. Participants with persistent cTnI or cTnT elevations, abnormal ECG or abnormal echocardiogram should undergo cardiology follow up.

The requirement to perform an ECG after elevations observed in Troponin T was not added to the protocol until version 9.0. Therefore, this ECG requirement related to cTnT elevation was not implemented as all participants enrolled under and participated in the protocol version 7.0 or earlier.

5.2.4 Echocardiogram (ECHO)

A local echocardiogram is to be performed within 24 hours of any of these events: an elevation of cTnI above the ULN (see Appendix 10.9 in the protocol for reference range), or when there is an elevation of cTnT above the ULN (see Appendix 10.9 in the protocol for reference range) or above the participant's baseline value if it was elevated, or when a participant has any signs or symptoms reflecting cardiac involvement, inclusive of new onset shortness of breath. If the echocardiogram is within normal limits, a repeat of the abnormal troponin value (cTnI or cTnT) should be obtained. For any of the situations above, it may be required to interrupt or discontinue further administration of IP. Participants with persistent cTnI or cTnT elevations, abnormal ECG or abnormal echocardiogram should undergo cardiology follow up.

The requirement to perform an ECHO after elevations observed in Troponin T was not added to the protocol until version 9.0. Therefore, this ECHO requirement related to cTnT elevation was not implemented as all participants enrolled under and participated in the protocol version 7.0 or earlier.

5.2.5 Body Weight

Body weight is planned to be collected at each visit scheduled in the protocol.

5.2.6 Laboratory test (hematology, biochemistry and urinalysis)

Safety laboratory tests will be done by a central laboratory from the screening to the end of the study. The scheduled visit and the list of clinical laboratory tests are described in the protocol.

5.2.7 Columbia-Suicide Severity Rating Scale (C-SSRS)

The C-SSRS will be performed by trained site staff via interview at screening, randomization, and all subsequent study visits. At screening, the "Screening" version is to be used to determine eligibility. During all subsequent visits, the "Since Last Visit" version is used to monitor on study suicidal ideation and behavior after the initial assessment. If possible, continuity of raters should be maintained across visits for each patient. The following five questions regarding suicidal ideation, six questions regarding suicidal behavior and question for non-suicidal self-injurious behavior will be used for analysis.

- Suicidal Ideation ('Yes' to any one of the below 5 questions for suicidal ideation)
 - Wish to be Dead (No/Yes)
 - o Non-Specific Active Suicidal Thoughts (No/Yes)

- Active Suicidal Ideation with Any Methods (Not Plan) without Intent to Act (No/Yes)
- o Active Suicidal Ideation with Some Intent to Act, without Specific Plan (No/Yes)
- o Active Suicidal Ideation with Specific Plan and Intent (No/Yes)
- Suicidal Behavior ('Yes' to any one of the below 5 questions for suicidal behavior)
- Preparatory Acts or Behavior (No/Yes)
 - Aborted Attempt (No/Yes)
 - Interrupted Attempt (No/Yes)
 - Actual Attempt (No/Yes)
 - Completed Suicide (No/Yes)
- Suicidal Ideation or Behavior ('Yes' to any one of the above 10 questions for suicidal ideation and behavior)
- Self-injurious Behavior Without Suicidal Intent (No/Yes)

5.3 Other Endpoints

5.3.1 Pharmacokinetics Endpoints

Relationship between measured- and model-based pharmacokinetic exposure parameters (e.g., C_{trough}, C_{ave, ss}) of ASP0367 and endpoints of efficacy, safety and pharmacodynamic biomarkers, as appropriate.

5.3.2 Pharmacodynamics Endpoints

Blood samples for PPARδ target gene expression assay

5.3.3 Biomarkers

Urine samples for TITIN

Blood samples for serum target proteins (ALDOA, CYC and FLNC)

6 STATISTICAL METHODOLOGY

6.1 General Considerations

Continuous data will be summarized descriptively including the number of participants (n), mean, standard deviation (SD), median, minimum and maximum. Categorical data will be summarized by frequencies and percentages. Percentages by categories will be based on the number of participants with no missing data, i.e. the percentages for the non-missing categories will add up to 100%.

There are 2 different groups defined based in the randomization group:

- ASP0367 any dose group: Participants randomly assigned to ASP0367.
- Placebo to ASP0367 group: Participants randomly assigned to placebo and who continue into the OLE and receive ASP0367.

Safety analysis and other summaries based on SAF will be presented by analysis group (ASP0367 any dose group or Placebo to ASP0367 group), unless specifically stated otherwise.

All data summarization and analyses will be performed using SAS® Version 9.4 or higher on Linux. Specifications for table, figures, and data listing formats can be found in the TLF specifications.

For continuous variables that are recorded as "<X", "<=X", ">X", or ">=X", the value of "X" will be used in the calculation of summary statistics if otherwise noted. This approach may result in a summary that reflects the presence of an analyte (such as troponin) when in fact the analyte was not detected but reported as less than the lower limit of detection by the assay.

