1 INTRODUCTION

This SAP contains technical and detailed elaboration of the principal features of the analysis described in the protocol and includes procedures for executing the statistical analysis to fulfil the objectives of the study.

The study was designed to be, and executed as, a double-blinded with an OLE. The OLE was removed from protocol version 9.0 and so, the use of the present tense is no longer accurate. In addition to the objectives and endpoints defined in Study 0367-CL-1201 protocol (core protocol), some additional objectives and endpoints specific to the Mayo Clinic (Minnesota) had been defined in Study 0367-CL-1201 [MAYO] Protocol. However, as there have been no participants recruited to the protocol from the Mayo sites, therefore there will be no SAP created. Until protocol version 7.0, the double-blinded period was 52 weeks and open label extension period was 24 weeks. However, from protocol version 8.0 onwards, the doubleblinded period was revised to 24 weeks and in protocol version 9.0 the OLE period was removed. Since no participants have been evaluated under protocol version 8.0 or later, two SAPs will be prepared: one for analyses up to 52 weeks of treatment (the double-blind part of the study), and the other one for analyses at the end of 76 weeks of treatment (the doubleblind part and the OLE part of the study). In analysis for the double-blind part and the OLE part of the study, participants assigned ASP0367 in the double-blinded period will be analyzed for through the double-blinded part and the OLE part of the study including followup visit, while participants switched from Placebo to ASP0367 in the OLE part will be analyzed in the OLE part only including follow-up visit.

This document is an analysis plan for 52 weeks (double-blinded part) including follow-up visit which correspond to protocol v7.0. However, inferential analyses for efficacy endpoints will be conducted at week 24 aligned with protocol v9.0.

Analyses for pharmacokinetic and pharmacodynamic (target gene expression and biochemical markers) endpoints, including exposure-response assessment, will be described in the separate analysis plan and this SAP only focus on efficacy and safety endpoints.

This document will be finalized prior to the database lock at the end of study. If there are any changes from the planned analyses in the final version of the SAP that impact the statistical analyses, then it will be documented in the CSR.

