5.4 Primary Safety Endpoints

5.4.1 Treatment Emergent Adverse Events (TEAEs)

AE collection begins after the ICF has been signed and continues until the follow up visit or 28 days after the final IP administration or when the participant is determined to be a screen failure. A TEAE is defined as an AE observed after starting administration of the IP to 28 days after the last dose of IP for double-blind treatment period of the study or moving to the OLE part, whichever comes first.

An IP-related TEAE is defined as any TEAE with a causal relationship of "yes" by the investigator.

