6 STATISTICAL METHODOLOGY

6.1 General Considerations

Continuous data will be summarized descriptively including the number of participants (n), mean, standard deviation (SD), median, minimum and maximum. Categorical data will be summarized by frequencies and percentages. Percentages by categories will be based on the

number of participants with no missing data, i.e. the percentages for the non-missing categories will add up to 100%.

There are 4 different groups defined based in the randomization group in double-blind treatment period of the study:

- ASP0367 30 mg: Participants randomly assigned to 30 mg of ASP0367 during double-blind treatment period.
- ASP0367 75 mg: Participants randomly assigned to 75 mg of ASP0367 during double-blind treatment period.
- ASP0367 any dose: Participants randomly assigned to 30mg or 75 mg of ASP0367 during double-blind treatment period.
- Placebo group: Participants randomly assigned to placebo during double-blind treatment period.

Summaries based on FAS (e.g. efficacy data) will be presented by analysis group (ASP0367 30 mg group, ASP0367 75 mg group or placebo group), unless specifically stated otherwise. Statistical model and inference based on FAS will be performed and obtained by analysis group. To control the family-wise type I error under the nominal significance level of 10% 2-sided, the hierarchical testing procedure in the following order (Comparison between ASP0367 75 mg and placebo; Comparison between ASP0367 30 mg and placebo) will be applied in the primary analysis.

Safety analysis and other summaries based on SAF will be presented by analysis group (ASP0367 30 mg group, ASP0367 75 mg group or placebo group), unless specifically stated otherwise.

All data summarization and analyses will be performed using SAS® Version 9.4 or higher on Linux. Specifications for table, figures, and data listing formats can be found in the TLF specifications.

For continuous variables that are recorded as "<X", "<=X", ">X", or ">=X", the value of "X" will be used in the calculation of summary statistics if otherwise noted. This approach may result in a summary that reflects the presence of an analyte (such as troponin) when in fact the analyte was not detected but report as less than the lower limit of detection by the assay.

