6.5 Analysis of Safety

Analysis population: SAF, Analysis group: 30, 75 mg of ASP0367, ASP0367 any dose group or placebo group

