6.5 Analysis of Safety

Analysis population: SAF, Analysis group: ASP0367 any dose group or Placebo to ASP0367 group

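### The 76-week SAP pools 30 mg and 75 mg in every safety table, so no planned table shows safety by dose after OLE entry or over cumulative exposure

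*SAP*

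**What the plan says.** There are two SAPs: one for the 52-week double-blind part and one for the whole period to week 76.

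**76-week SAP.** Section 6.1 states: "There are 2 different groups defined based in the randomization group". One of these is "ASP0367 any dose group: Participants randomly assigned to ASP0367"; the other is participants randomised to placebo who went on to receive ASP0367 in the OLE. Safety summaries are "presented by analysis group (ASP0367 any dose group or Placebo to ASP0367 group), unless specifically stated otherwise". Section 6.5 repeats the choice: "Analysis population: SAF, Analysis group: ASP0367 any dose group or Placebo to ASP0367 group". The exception clause is never used to produce a 30 mg or 75 mg table.

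**52-week SAP.** Section 6.1 keeps the doses apart, for example "ASP0367 30 mg: Participants randomly assigned to 30 mg of ASP0367 during double-blind treatment period", and section 6.5 reads "Analysis population: SAF, Analysis group: 30, 75 mg of ASP0367, ASP0367 any dose group or placebo group". Its scope is limited: "This document is an analysis plan for 52 weeks (double-blinded part) including follow-up visit which correspond to protocol v7.0". Section 5.4.1 ends the treatment-emergent window at "28 days after the last dose of IP for double-blind treatment period of the study or moving to the OLE part, whichever comes first". Sections 6.5.2, 6.5.2.1 and 6.8.1 likewise stop laboratory, liver and by-visit data at the OLE.

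Both current versions are dated 9 July 2024. Neither explains why the dose columns are dropped in the longer analysis.

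**The concern.** The longest exposures in the programme are summarised with the least dose detail. Safety through week 24 and to the end of study is a primary endpoint (SAP section 2.1), and Protocol section 4.3 says the two doses, which differ 2.5-fold (75/30), were chosen so that a dose response could be evaluated. Protocol section 2.3.1.3 names heart and skeletal muscle toxicity as important potential risks. Section 2.3.1.1 describes dose-dependent proliferative findings in rats and gives the carcinogenicity concern as the reason dosing is now limited to 6 months. Exposure beyond 6 months is therefore scarce. Whether events follow dose is one of the few ways to judge them in a period without a placebo comparison, and a pooled column does not allow that judgement.

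**Working it through.** **1. Arm sizes.** The only powered figure in the plan concerns the 6MWT: n = 2(z₀.₉₅ + z₀.₈₀)² × SD²/Δ² = 2 × (1.645 + 0.842)² × 55²/45² = 18.5, so 19 per group, as stated. The plan then goes to 60 for the interim analysis and 66 for dropout; 66/3 = 22 per arm. No safety table has a size calculation. The interim that led to the futility recommendation had 33 participants; 33/3 = 11 per arm if allocation was even, which is an assumption. The range used below is therefore 11 to 22 per dose. The number who entered the OLE is not given and would be smaller.

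**2. Which period is tabulated by dose.**

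| Period | 52-week SAP | 76-week SAP |
|---|---|---|
| Double-blind, up to week 52 | 30 mg, 75 mg, any dose, placebo | any dose |
| After OLE entry, about week 52 to 76 plus 28 days | not covered | any dose; placebo to ASP0367 |
| Cumulative, first to last ASP0367 dose plus 28 days | not covered | any dose; placebo to ASP0367 |

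The last two rows have no 30 mg or 75 mg column in either plan.

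**3. Effect of pooling on the visible rate.** Pooled rate = (n₇₅p₇₅ + n₃₀p₃₀)/(n₇₅ + n₃₀), which is (p₇₅ + p₃₀)/2 with equal arms. The documents give no event rates, so these are illustrative:

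- 10% and 0%: pooled 5%
- 20% and 0%: pooled 10%
- 30% and 0%: pooled 15%
- 20% and 5%: pooled 12.5%

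An event confined to one dose is halved.

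**4. Effect of pooling on seeing the event at all.** P(at least one event) = 1 − (1 − p₇₅)ⁿ(1 − p₃₀)ⁿ. For 20% and 0% this is 1 − 0.8¹¹ = 91.4% at 11 per dose and 1 − 0.8²² = 99.3% at 22. It is the same whether the columns are pooled or split.

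**5. Size in participants.** For 20% against 5%, the difference between doses is 0.15 × 11 = 1.65, about 2 participants, at 11 per dose, and 0.15 × 22 = 3.3 at 22.

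**6. What separate columns could show formally.** Power of Fisher's exact test for 75 mg against 30 mg, two-sided 0.10:

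| True rates | 11 per dose | 22 per dose |
|---|---|---|
| 20% vs 0% | 16% | 46% |
| 20% vs 5% | 10% | 26% |
| 30% vs 5% | 27% | 61% |

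Splitting restores attribution to dose but gives little formal power.

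**The case against.** The best case for leaving the plan alone has four parts.

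- **Most exposure is already shown by dose.** For up to 52 weeks of randomised, placebo-controlled treatment, the 52-week SAP reports adverse events, events of special interest, troponin, liver categories and QTcF by dose. This stands, and it confines the gap to the OLE period and the cumulative summary.
- **There are other routes to dose information.** The Protocol lists adverse event data (section 9.4.3.1), an unblinded DSMB reviews safety (section 10.1.5.1.1), and exposure-response is deferred to a separate plan. These count, but they are not summary tables from which a reader of the study report can judge a dose pattern. The separate plan and the table specifications are not available here.
- **Randomised dose may not be the dose taken in the OLE.** The documents do not state the OLE dose. The original design carried one selected dose forward (Protocol section 4.2.1), and the compliance formula changes from three tablets in the 52-week SAP to an unspecified number per day in the 76-week SAP. If the doses differed, columns by randomised dose alone could misattribute OLE events. This is the strongest point. It shapes the remedy, but the SAP does not offer it as the reason for pooling.
- **No rule is broken.** The Protocol leaves data after week 24 to a separate SAP and sets no column layout. That is correct: this is a gap in reporting, not a contradiction.

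**Conclusion.** The point holds in a limited form. A dose relation that emerges after OLE entry, or over cumulative exposure to week 76, cannot be read from any safety table planned in the two SAPs. The visible rate of an event confined to one dose is halved under equal allocation.

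A reader might infer three stronger things that the documents do not support:

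- **That a dose-related toxicity would go unseen.** Every event is still counted in the pooled column, and the chance of recording at least one is unchanged.
- **That the long-term data can support no statement about safety by dose.** They can, up to week 52, through the companion SAP.
- **That a difference of 3 to 4 participants would be concealed.** That assumes the planned 22 per arm. With about 11 per arm, the same illustrative rates give about 2, and fewer among those who entered the OLE.

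The conclusion rests on equal allocation, illustrative event rates and an unknown number entering the OLE. None of these changes the finding that the by-dose view is absent.

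**What to change.** In the 76-week SAP:

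- In section 6.1, define 30 mg and 75 mg groups by randomised dose beside the any-dose group. The 52-week SAP already has the definitions.
- Add these columns to the section 6.5 tables, at least for adverse events, events of special interest, troponin and CK, and liver categories.
- State the dose taken in the OLE, including for participants who came from placebo. Where it differs from the randomised dose, present OLE-period events by the dose being taken at onset, with a footnote.

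The cost is two columns using existing definitions and, if doses differed, one derived variable for dose at onset. The downside is small denominators, so the columns should be labelled descriptive and carry no tests. If the SAP is not reopened, the added tables can be recorded in the study report as a change from the planned analyses, as section 1 of the SAP provides.
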